### 6.4.2 Secondary Efficacy Variable – Overall Survival at 24 months

The secondary efficacy variable is survival at 24 months after implant expressed as simple proportion (patients alive on the MVAD® pump divided by endpoint eligible patients). The overall survival at 24 months post implant will be presented as a simple proportion; that is, the point estimate will be  $n/N$ ; where  $N$  is the total number of patients included in the analysis set; and  $n$  is the number of patients alive by Relative Study Day 730 (lower bound of the 24 month visit).

Patients who are lost to follow-up or who withdraw consent prior to Relative Study Day 730 will be excluded from both denominator and numerator when computing the simple proportion. Patients with transplants, explants for recovery or exchanges (to a device other than the MVAD® Pump) prior to Relative Study Day 730 will be included in the denominator for this analysis, with status identified at time of procedure. If there are any patients who are eligible for analysis but for whom the primary endpoint cannot be assessed, they will be excluded from both denominator and numerator for this analysis.

### 6.4.3 Additional Efficacy Variables

#### 6.4.3.1 Overall Survival (Time to Death)

Time to death (TTD) is defined as the time from date of implant until date of death on device (in days). If a patient had a transplant, explants for recovery, exchanges (to a device other than MVAD® Pump) prior to endpoint, and any withdrawal or lost to followup will be censored at the time of this event date. For each patient that remains alive on device, TTD

will be censored at the time of last contact date known to be alive (contacts considered in the determination of last contact date would include but not limited to scheduled visit dates, adverse event date, and last known alive date).

Time to Death (TTD) = Date of event/censor – Date of Implant + 1.

#### 6.4.3.2 Health Status, as measured by EuroQol EQ-5D-5L

The EuroQol-5D-5L (EQ-5D-5L), an assessment of general well-being, will be utilized. Pre-implant assessment will be performed at screening/pre-implant (when feasible) and month 1, 3, 6, 12, 18, and 24.

The EQ-5D-5L includes a descriptive system that comprises 5 dimensions of health status and a VAS scale (referred to as EQ VAS) that records the respondent's self-rated health status. The 5 dimensions of health status are

- Mobility (M)
- Self-care (S)
- Usual activities (U)
- Pain/discomfort (P)
- Anxiety/depression (A)

The EQ VAS value and the change from baseline will be tabulated by time point.

The EQ VAS data at screening (baseline), at each post implant visit (post baseline), and change from baseline (visit value – baseline value) will be calculated for each patient.

#### 6.4.3.3 Health Status, as measured by Kansas City Cardiomyopathy Questionnaire (KCCQ)

The KCCQ, a disease specific 23-item, self-administered instrument that quantifies physical function, symptoms (frequency, severity, and recent change), social function, self-efficacy and knowledge and quality of life. Patients will complete the KCCQ at screening/pre-implant (when feasible) and month 1, 3, 6, 12, 18, and 24.

The KCCQ is composed of 15 questions. The questions are grouped to reflect clinically relevant domains: physical limitation (question 1a-1f), symptom stability (question 2), symptom frequency (questions 3, 5, 7, 9), symptom burden (questions 4, 6, 8), self-efficacy (questions 10, 11), quality of life (questions 12, 13, 14), and social limitation (question 15a-15d). To facilitate interpretability, three summary scores were developed, overall summary score, total symptom score, and clinical summary score. Further details of the KCCQ determination is presented in the Appendix.

Scale scores for the total and for each domain (physical limitation, symptoms, self-efficacy, social limitation, quality of life, functional status, and clinical summary) will be calculated for each patient at each time point. The change from baseline (visit value – screening visit

value) will be calculated for each patient. The values and the change from baseline will be tabulated by time point.

#### 6.4.3.4 *Functional status, as measured by NYHA*

Determination of NYHA classification will be performed by an independent assessor (defined as a physician or qualified physician assistant (PA), registered nurse (RN) or nurse practitioner (NP) not directly involved with this clinical trial). NYHA will be captured at screening/pre-implant and month 1, 3, 6, 12, 18, and 24. The number of patients by NYHA Class will be determined at each time point. The denominator will be the number of patients on the device at the given time point and completed the assessment form.

#### 6.4.3.5 *Functional status, as measured by 6-minute walk*

Subjects will complete a six minute walk test at screening/pre-implant and month 1, 3, 6, 12, 18, and 24. Missing data in patients who did not perform the 6-minute walk due to early termination will not be imputed. Those patients will be excluded from the analysis. Missing data in patients who were medically unable to or indicated that they could not perform the 6-minute walk task will be imputed to zero (0). If a patient missed a visit or the associated CRF page was not filled out at a visit then no imputation will be done.

#### 6.4.3.6 *National Institutes of Health Stroke Scale (NIHSS)*

NIHSS assessments will be obtained screening/pre-implant and month 1, 3, 6, 12, 18, and 24, by a trained individual. In addition to screening/pre-implant assessment, NIH Stroke Scale is required in the event of a stroke. After a stroke, a follow-up NIH Stroke Scale is required at 12 weeks (+/-7 days), and 24 weeks (+/-7 days) after the event to document any deficits. The total raw NIHSS score will be used for reporting purposes.

#### 6.4.3.7 *Modified Rankin Scale (MRS)*

The Modified Rankin Scale (MRS) will be obtained screening/pre-implant and month 1, 3, 6, 12, 18, and 24, by a trained individual. MRS will be required in the event of a stroke. After a stroke, a follow-up MRS score is required at 12 weeks (+/-7 days), and 24 weeks (+/-7 days) after the event to document any deficits. An MRS score greater than 3 will be used to suggest the presence of neurological deficit after a stroke.

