### Modified Rankin Scale (MRS)

Modified Rankin Scale is a valid estimate of global disability based on a patient's ability to independently perform day-to-day activities of daily living. An MRS score will be obtained using a structured interview created by Wilson et al. When used with the structured interview, the MRS is highly reliable. An MRS score greater than 3 (i.e., 4 or 5) will be used to suggest the presence of neurological deficit after a neurological event. If the screening/ pre-implant (pre-existing) score is 4, then a score of 5 will be used to define neurologic deficit after a neurological event.

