#### **5.2 Changes from the Analyses Planned in the Protocol/CIP**

Due to the early stop of the protocol, fewer than 15 subjects were enrolled. As such, summary statistics are of little use. Therefore, case studies for each subject enrolled and followed will be presented and summary statistics are no longer planned.

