#### 8.7.3.7 *Modified Rankin Scale*

Results of the MRS by category (MRS Score of 0, 1, 2, 3, 4, 5, and 6) at each scheduled visit will be tabulated using counts and percentages. A shift table of change from stroke to 12 weeks post-stroke and of change from stroke to 24 weeks post-stroke will be presented using counts and percentages.

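### SAP 6.4.3.7 omits, without declaring it, the protocol's exception for a pre-implant modified Rankin score of 4, so a subject unchanged at 4 after a stroke is labelled a deficit

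*SAP*

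**What the plan says.** Protocol 17.4, under Modified Rankin Scale, gives the rule in two parts. The general part reads "An MRS score greater than 3 (i.e., 4 or 5) will be used to suggest the presence of neurological deficit after a neurological event". The exception follows: "If the screening/ pre-implant (pre-existing) score is 4, then a score of 5 will be used to define neurologic deficit after a neurological event".

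SAP 6.4.3.7 keeps only the general part: "An MRS score greater than 3 will be used to suggest the presence of neurological deficit after a stroke". It says nothing there about the pre-implant score, although the same section schedules one: "The Modified Rankin Scale (MRS) will be obtained screening/pre-implant and month 1, 3, 6, 12, 18, and 24".

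SAP 8.7.3.7, which sets out the MRS analysis, does not supply the exception either. It plans "Results of the MRS by category (MRS Score of 0, 1, 2, 3, 4, 5, and 6) at each scheduled visit" and "A shift table of change from stroke to 12 weeks post-stroke and of change from stroke to 24 weeks post-stroke".

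SAP 5.2, the place for departures from the protocol, reports only the consequence of stopping early: "Due to the early stop of the protocol, fewer than 15 subjects were enrolled", so that "case studies for each subject enrolled and followed will be presented and summary statistics are no longer planned". It does not mention the MRS rule.

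**The concern.** Protocol 17.4 describes the MRS as a measure of global disability, so it is not specific to stroke. The trial enrols patients in NYHA class IIIB or IV, some of them dependent on inotropes or a balloon pump (Protocol 8.2). It is plausible that some would score 4 before implant because of heart failure alone, and the protocol's exception provides for them. Without it, disability that was present before the pump and has not changed is labelled as a deficit following a stroke.

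What is at stake is the wording of individual case studies. An author stating whether a stroke left a deficit has two signed-off rules that can give opposite answers for the same patient. With so few subjects, a single wrong label is visible and is not diluted by others.

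**Working it through.** There is no figure in the plan to reproduce. The check is a comparison of the two rules, followed by a rough size.

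**Comparison.** Take every pair of pre-implant score (0 to 5) and post-stroke score (0 to 5), which gives 6 × 6 = 36 pairs.

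- SAP rule: deficit if the post-stroke score exceeds 3.
- Protocol rule: the same, except that a pre-implant score of 4 requires a post-stroke score of 5.

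Neither document addresses a pre-implant score of 5, so the general rule is applied there.

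| Pre-implant | Post-stroke | Pairs | SAP | Protocol |
|---|---|---|---|---|
| 0–5 | 0–3 | 24 | no deficit | no deficit |
| 0–3 or 5 | 4 | 5 | deficit | deficit |
| 4 | 4 | 1 | **deficit** | **no deficit** |
| 0–5 | 5 | 6 | deficit | deficit |

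The pairs sum to 24 + 5 + 1 + 6 = 36. The rules disagree in exactly one of them, the subject who stays at 4.

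**Where the label is used.**

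- SAP 8.7.3.7 tabulates raw MRS categories and shifts from the score at the time of stroke. No yes/no deficit variable is derived.
- The NIHSS is reported as a raw total (SAP 6.4.3.6).
- Neurological dysfunction is defined by examination, diagnostic tests and imaging (Protocol 17.9), adjudicated on INTERMACS definitions (Protocol 16.2.3), and reported by type of event (SAP 8.8.2.1). The MRS plays no part in it.
- SAP 5.2 replaces the summaries with case studies. These are the only remaining place where the label could appear.

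**Size.** Inputs:

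- at most 14 subjects (SAP 5.2)
- 0.15 strokes per patient-year (Protocol 10.1.4.1)
- 1.0 to 1.6 years of support per subject (assumption)
- 10 to 30% of subjects at 4 before implant (assumption; the documents give no distribution)

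Expected strokes = rate × subjects × years:

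- low: 0.15 × 14 × 1.0 = 2.1
- high: 0.15 × 14 × 1.6 = 3.36

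Expected strokes in subjects with a pre-implant score of 4:

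- low: 2.1 × 0.10 = 0.21
- high: 3.36 × 0.30 = 1.01

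That is about 0.2 to 1.0. It bounds the number affected, because the post-stroke score must also be exactly 4. A subject who moves to 5, or to 3 or below, is labelled the same way by both rules.

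**The case against.** The strongest case against is that nothing reported depends on this sentence. The SAP says only that the score will suggest a deficit. No planned output contains the classification. The pre-implant score is scheduled, and listings of all case report form data are planned (SAP 7.1), so a reader of a case study could see an unchanged 4. The documents do not show that any enrolled subject scored 4 before implant or had a stroke.

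Most of this stands, and it sets the severity. It does not make the SAP rule right. A stated classification that gives a result the protocol rules out, with no declared change, is an error even when rarely triggered. The planned shift table would not expose it, because it starts from the score at stroke and does not show the pre-implant score.

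Two stronger readings are tempting. A reader might infer that the neurological results would attribute existing disability to stroke. The documents do not support that: stroke and neurological dysfunction are defined and adjudicated without the MRS, and the event has already been classified before this rule applies. A reader might also size the problem on the planned 60 subjects: 0.15 × 60 × 1.0 to 1.6 = 9.0 to 14.4 strokes, and 10 to 30% of those is about 1 to 4. The current SAP puts enrolment below 15, so that calculation describes a trial that did not take place.

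**Conclusion.** Wrong as written, low severity. SAP 6.4.3.7 contradicts Protocol 17.4 for one of 36 score pairs, a subject at 4 before implant and 4 after a stroke, and the difference is not declared. The effect is limited to the deficit label in individual case studies. Survival endpoints, sample size, error rates, stroke counts and INTERMACS event results are untouched.

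On the assumed follow-up and the assumed share at 4 before implant, at most about 0.2 to 1.0 strokes would be affected, and fewer if the post-stroke score does not stay at 4. Both assumed inputs scale the answer in proportion, and the documents do not narrow either.

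Two smaller differences sit in the same sentence. The SAP applies the rule after a stroke, where the protocol applies it after any neurological event. The SAP's threshold has no upper limit and its tabulated categories run to 6, while the protocol names 4 or 5. One rewording can settle both.

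**What to change.** Reword SAP 6.4.3.7 to match the protocol: after a neurological event, a score of 4 or 5 suggests a deficit, except that where the pre-implant score was 4, only a 5 counts. It must be written as an exception. Adding a score of 5 as a further alternative to the general threshold would change nothing, because 5 already exceeds 3 and an unchanged 4 would still be labelled a deficit.

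If the simpler rule is intended, say so in SAP 5.2 and justify it.

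The cost is one sentence. The pre-implant MRS is already scheduled (Protocol 9.1.9, where feasible, and 17.1.1), so no new data are needed. Any case study that states a deficit should give the pre-implant and post-event scores side by side.

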## 6.5 Drug Concentration Measurements and Pharmacokinetic Parameters

Not applicable to this study.

## 6.6 Safety Variables

### **6.6.1 Extent of Exposure and Compliance to Study Treatment**

This is a device study; all qualified patients are to be implanted with the investigational device in the hospital. Timing of the implantation and associated parameters will be recorded on the CRFs.

### **6.6.2 Adverse Events**

The investigator's verbatim term for all adverse events (AEs) will be mapped to system organ class (SOC) and preferred terms using the current version of the Medical Dictionary for Regulatory Activities (MedDRA).

An AE in this study is any untoward medical occurrence, unintended disease or injury or any untoward clinical signs in subjects, users or other persons whether or not related to the investigational medical device. This includes events related to the investigational medical device. This includes events related to the procedures involved (any procedure in the clinical investigation plan). For users or other persons this is restricted to events related to the investigational medical device. From the time the informed consent form is signed adverse events will be collected. Only AEs occurring while on the device are considered treatment-emergent. In the event of an explant for transplant or recovery, adverse events will be collected until the induction of anesthesia for explant. AEs occurring after the device has been turned off in lieu of surgical explant will not be collected. In the event of an explant for an exchange for another HeartWare MVAD® system, adverse events will be collected throughout the subject's participation on the trial. In the event of an explant for exchange for a non HeartWare MVAD® system, adverse events will be collected until the induction of anesthesia for exchange.

In addition, INTERMACS-defined AEs occurring during the study will be recorded. The definition for all INTERMACS-defined AEs can be found in Appendix 17.9 of the protocol. The category of other adverse events will be those adverse events that were unable to be reported into an INTERMACS-defined adverse event category. For the INTERMACS-defined adverse events, the number of events per person-year will be calculated.

For each event, the potential etiology of the event will be determined by the investigator and categorized as:

1. Related to MVAD® Procedure
2. Related to MVAD® System
3. Undetermined
4. Subject Condition
5. Other

Any event categorized as related to MVAD® procedure or related to MVAD® system will be considered an adverse device event (ADE). Any event categorized as subject condition, undetermined or other will be considered a non adverse device event (non ADE).

For an event where the relationship is missing, the relationship will be considered related for analysis purposes.

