### 10.2.2 Possibly related

Is defined as an AE which might be due to the use of the investigational device. An alternative explanation (e.g., concomitant drug(s), concomitant disease(s)) is inconclusive. The relationship in time is reasonable; therefore the causal relationship cannot be excluded.

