#### *6.6.2.1 Non Adverse Device Event (non ADE)*

Adverse events not related to the use of the investigational medical device. This includes events reported due to the subject condition, not able to be determined to be related to the medical device, or other. A non adverse device event (non ADE) will be considered emergent if the onset of the event is on or after the start of anesthesia for the implant surgery.

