Adverse events potentially related to study device are defined as a subset of adverse events with a relationship to study device of either possible related or related. Events with missing relationship assessment will be included as potentially related to study device.

No statistical inference will be performed on adverse events.

Listings will be presented by patient for all adverse events as well as for each INTERMACS definition, UADEs, SAEs, adverse events associated with death, and adverse events leading to study device explant/exchange.

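### SAP 6.6.2 classes every adverse event of undetermined cause as not device related, against the SAP's own rules for missing and possible relationships and the protocol's possibly-related level

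*SAP*

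**What the plan says.** SAP 6.6.2 has the investigator assign each event to one of five etiologies: MVAD procedure, MVAD system, undetermined, subject condition or other. The first two make an ADE: "Any event categorized as related to MVAD ® procedure or related to MVAD ® system will be considered an adverse device event (ADE"). For the other three: "Any event categorized as subject condition, undetermined or other will be considered a non adverse device event (non ADE"). SAP 6.6.2.1 defines non-ADEs as events not related to use of the device and repeats the assignment: "This includes events reported due to the subject condition, not able to be determined to be related to the medical device, or other".

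Immediately after the etiology rule, SAP 6.6.2 deals with blanks: "For an event where the relationship is missing, the relationship will be considered related for analysis purposes".

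SAP 8.8.2.2 uses a different scale. It defines events potentially related to the device as those with a "relationship to study device of either possible related or related", and adds events whose relationship is missing.

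Protocol 10.2 has three levels: not related, possibly related and related. For the middle level, Protocol 10.2.2 says "An alternative explanation (e.g., concomitant drug(s), concomitant disease(s)) is inconclusive" and "The relationship in time is reasonable; therefore the causal relationship cannot be excluded".

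SAP 5.2 (version 2.0) records the early stop, replaces summary statistics with a case study per subject, and leaves the rules in 6.6.2 and the table lists in 8.8.2 as they were. SAP 7.1 still promises listings of CRF data and derived variables.

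**The concern.** The five etiology categories have no level for a possible relationship. An investigator who cannot settle the cause has *undetermined* available, and that entry is turned into a statement that the event is not device related. A blank is turned into the opposite. If both rules apply to one data field, answering a query on a blank (Protocol 15.2.2 provides for such queries) with *undetermined* would move the event from related to non-ADE without any new evidence about the pump.

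This is the first clinical use of the device, and safety is a stated objective. The protocol's own list of anticipated events (10.1.4.1) marks 31 of 32 entries as possibly device related; only aspirin sensitivity is marked no. Defaulting unattributed events to not related runs against that expectation. With few subjects described one by one, a single label can change how a subject's course reads.

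**Working it through.** The plan states no figure on this point, so there is none to reproduce. The check is a comparison of rules, followed by the algebra of the difference.

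**How each rule scores the same record**

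| Record | SAP 6.6.2 and 6.6.2.1 | SAP 8.8.2.2 | Protocol 10.2 |
|---|---|---|---|
| Attributed to the MVAD system | ADE | potentially related | related |
| Relationship missing | related | potentially related | no rule |
| Undetermined; timing reasonable, alternative inconclusive, might be due to the device | non-ADE | potentially related, if scored as possible | possibly related |
| Undetermined; those conditions not met | non-ADE | no rule | does not meet possibly related |

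The third row is where the rules conflict. The fourth shows that *undetermined* and *possibly related* are not the same set.

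**Direction and size**

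Let R be the events attributed to system or procedure, M those with a missing relationship, U those called undetermined, and s the share of U that meets Protocol 10.2.2 (0 ≤ s ≤ 1).

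- Counted as device related under SAP 6.6.2: A = R + M.
- Counted when possible is grouped with related: B = R + M + sU.
- Shortfall: B − A = sU. As a share of B: sU / (R + M + sU).

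Because s and U cannot be negative, A never exceeds B. The shortfall is zero if U = 0 or s = 0, and U at most.

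**Illustration only.** R, M, U and s are all assumed, since the documents give none of them. With R = 40 and M = 2, A = 42:

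| U | s = 0 | s = 0.5 | s = 1 |
|---|---|---|---|
| 5 | 0% | 2.5/44.5 = 5.6% | 5/47 = 10.6% |
| 10 | 0% | 5/47 = 10.6% | 10/52 = 19.2% |
| 20 | 0% | 10/52 = 19.2% | 20/62 = 32.3% |

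With s = 1 and U from 5 to 20, R = 20 gives 5/27 = 18.5% to 20/42 = 47.6%, and R = 60 gives 5/67 = 7.5% to 20/82 = 24.4%. The spread shows how far the answer depends on inputs that the documents do not supply.

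**The case against.** There are five serious objections.

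1. *The tables are no longer planned.* A reader might infer that the device-related tables are understated. SAP 5.2 does not support that: summary statistics are dropped, and the lists in 8.8.2 survive only as text. For the same reason, applying the anticipated stroke rate to the planned 60 subjects does not describe this trial. This stands and limits where the rule has effect; the labels in listings and case studies remain.
2. *Undetermined is not possibly related.* Protocol 10.2.2 also asks for reasonable timing and an inconclusive alternative. This stands: some undetermined events, perhaps none, would qualify. It does not justify calling all of them not related.
3. *The protocol does not say that possibly related events are ADEs.* Protocol 10.1.3.1 speaks only of related events; the grouping of possible with related is in SAP 8.8.2.2. This stands. The conflict is therefore partly within the SAP, and partly with the protocol's causality scale rather than its ADE definition.
4. *Etiology and relationship may be separate fields.* The CRF is not among the documents. If they are separate, the contrast between a blank and *undetermined* is less direct. But the missing-relationship rule follows the etiology rule within 6.6.2, with nothing to say that it concerns another field, and 6.6.2.1 still equates undetermined with not related.
5. *The adjudicated outputs may follow another scale.* No section says which causality categories the CEC uses. This stands, so the point is not made for adjudicated labels.

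A reader might also infer that undetermined events disappear. They do not: they stay among all adverse events and non-ADEs, and listings show all of them. Only the device attribution is affected.

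**Conclusion.** The concern holds in a limited form. The SAP turns an unsettled cause into a finding of no device relationship, while it treats a missing relationship as related and elsewhere groups possible with related. Relative to those rules and to Protocol 10.2.2, the effect runs one way: fewer device-related labels, or the same number.

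The size cannot be stated. It is sU, from zero up to the number of undetermined events, and the documents give neither quantity; the percentages above rest wholly on assumed inputs. As the plan now stands, what is affected is the ADE and non-ADE labelling in listings and case studies of fewer than 15 subjects. The section 8 tables would be affected only if they were produced after all.

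**What to change.** - In SAP 6.6.2 and 6.6.2.1, stop classing *undetermined* as not related. Treat it, like a missing relationship, as potentially device related (the 8.8.2.2 grouping).
- Show undetermined as its own category, apart from definite system or procedure attribution, so that it is not folded into definite ADEs.
- State one mapping of the five etiology categories to the three levels of Protocol 10.2, and reconcile 6.6.2 and 6.6.2.1 with 8.8.2.2, including where a missing relationship belongs.
- State that this rule governs the listings and case studies.

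The cost is SAP wording and one derivation, with no new data. The downside is a somewhat higher potentially device-related count, which may include undetermined events that do not meet Protocol 10.2.2; in the notation above, up to (1 − s)U of them. The separate category keeps these visible.
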